5.3 Supportive Care

Standard supportive therapies at the discretion of the treating radiation oncologist.

5.4 Early Study Termination

This study can be terminated at any time for any reason by the PI-sponsor. If this occurs, all subjects on study should be notified as soon as possible. Additional procedures and/or follow up should occur in accordance with Section 10.7, which describes procedures and process for prematurely withdrawn subjects.

6 PATIENT ASSESSMENTS

Assessment	Pre-Tx.	Follow-up
Consent	X	
History/Physical	X	X ^a
Complete Blood Count (no differential)/CMP	X	
Breast imaging (mammogram minimum)	X ^g	X ^a
Core Biopsy/Fiducial Markers	X ^b	
Planning MRI	X	
Surgical Excision		X ^c
Acute Toxicity Evaluation		X ^d
Cosmetic Evaluation Form/Digital Photographs/QOL	X ^e	X ^e
Clinical Outcomes		X ^a
Serum Collection	X ^f	X ^f

- Physical exam by member of oncology team recommended every 4-6 months for 2 years, every 6 months through year 5 and annually years 5-10. Bilateral mammogram recommended at least annually.
- Verify placement of a biopsy clip at diagnostic procedure.
- Within 2-4 days following radiation (up to 7 allowed if needed – see below).
- Appointment by a radiation oncology physician/mid-level provider 1-2 months post-radiation.
- At baseline (prior to treatment), six months and one year after treatment and then annually for 2 additional years. To be filled out by both patient and physician/mid-level provider. Digital photographs at the same time points and at investigator’s discretion.
- 2 lavender tubes drawn prior to radiation therapy and post radiation therapy (before surgery)
- Mammogram will not be repeated if one has been obtained within 6 months of signed study consent. Mammography does not need to be repeated unless clinically indicated.

6.1 Pretreatment Evaluations/Management

Prior to treatment each patient will be required to have a complete history and physical including signed informed consent, basic clinical laboratory studies, staging and a biopsy demonstrating ductal carcinoma in situ or invasive breast carcinoma.

Assessment of the tumor by physical exam and mammogram (further imaging at radiologist/physician discretion) should include tumor measurements. Each patient will complete a baseline cosmetic evaluation as will her physician/mid-level provider. QOL measures will also be assessed. Prior to study treatment, placement of a biopsy clip at the time of diagnostic biopsy will be verified as this will serve as a fiducial marker (described in section 8.2) to assist in radiotherapy localization. MRI and CT of the affected breast will then be completed in Radiation Oncology for radiation treatment planning.

6.2 Screening Examination

The screening examination will take place up to 45 days before study treatment. An informed consent must be signed by the patient before any screening procedure takes place. If however, standard of care evaluation procedures have been obtained and are within the screening evaluation time points, the SOC procedures do not need to be repeated and may be included in the screening examination.

6.3 End of Treatment/Follow-up Period

Lumpectomy will be completed 2-4 days (though up to 7 days will be allowed for logistical constraints without considering this a protocol deviation) following RT delivery. Tissue will be processed as described below in section 8.1. A surgical margin will be considered negative if there is no ink on tumor. The patient will be assessed by a Radiation Oncology physician/mid-level provider within 2 months after preoperative treatment, to evaluate for treatment toxicity. Subjects will then go on to complete systemic therapy as indicated or proceed to conventional radiation.

Subjects will be seen weekly during conventional treatment as is standard procedure in our department. Follow-up after conventional radiation will follow national guidelines and includes a history and physical every 4-6 months for the 1st 2 years, every 6 months to a year through year 5 and annually through year 10. Mammograms will be obtained at least annually. Other laboratory or radiographic studies will be obtained as directed by patient symptoms or physical exam. Quality of life and cosmetic assessments, physician/mid-level provider and patient, will be performed at 6 month, 1 year, and then annually through 3 years of follow-up as will digital photographs. Locoregional recurrence will be monitored on protocol at each follow-up visit.

6.4 Early Withdrawal of Subject(s)

6.4.1 Criteria for Early Withdrawal

Subjects may voluntarily withdraw from the study at any time. The PI may also withdraw a subject from the study at any time based on his/her discretion. Reasons for PI-initiated withdrawal may include, but is not limited to the following:

- Adverse events
- Abnormal laboratory values
- Abnormal test procedure results
- Protocol deviation
- Administrative issues
- Disease progression
- Pregnancy

6.4.2 Follow-up Requirements for Early Withdrawal

Standard of care follow up will adhered to.

7 Statistical Considerations

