A treatment plan utilizing arc therapy, or multiple conformal beams, or intensity-modulated therapy, or a combination of these techniques will then be designed. The beam arrangement can be organized in any fashion provided that the dose constraints listed below are met. The dose will be normalized to provide a desired coverage (95% to 98%) to the CTV. Subjects will receive a single fraction of 7 Gy.

Dose coverage (taken with some modifications to account for the single-dose preoperative delivery technique from the ongoing NRG phase III trial evaluating concurrent boost) will be considered appropriate as follows:

Target volume (CTV): prescribed dose covers >90% of the CTV without exceeding maximum dose of 110% of prescribed dose

Normal breast: <30% of the whole breast reference volume should receive 50% or more of the prescribed dose and <15% of the whole breast reference volume should receive the prescribed dose

Contralateral breast: the contralateral whole breast reference volume should receive <10% of the prescribed dose to any point

Lungs: Mean lung dose <3.6Gy, V5<10%

Heart: Mean should not exceed 50cGy, no point should receive greater than 4Gy, Dose to 1cc <2Gy

Thyroid: maximum point dose < 10% of the prescribed dose

Brachial plexus: no point in the brachial plexus should receive more than 10% (1Gy maximum) of the prescribed dose.

Skin dose: 1) Maximum dose will not exceed prescription dose. 2) Dose to 1cc: <6Gy (85% prescription)

Cord: maximum dose to 1 cc should be 1 Gy.

In addition, a low dose survey will be performed to ensure no unanticipated regions are receiving inappropriate dose.

Target Localization and Treatment Delivery:

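### Sections 6.4.1 and 6.4.2 let the PI withdraw a boosted woman for an adverse event and then drop her cosmesis assessments, so the good/excellent rate may be biased upward, and 7.1 has no rule for a missing score

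*Combined protocol and SAP*

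**What the plan says.** The study treatment is given once: "Subjects will receive a single fraction of 7 Gy" (Section 5.2). The cosmesis evaluation, photographs and quality of life fall due "At baseline (prior to treatment), six months and one year after treatment and then annually for 2 additional years" (Section 6, assessment table footnote).

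Section 6.4.1 states: "The PI may also withdraw a subject from the study at any time based on his/her discretion". The list of reasons is open ("Reasons for PI-initiated withdrawal may include, but is not limited to the following") and includes adverse events. It does not distinguish withdrawal before the boost from withdrawal after it. Section 6.4.2 consists of one sentence: "Standard of care follow up will adhered to".

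Section 6.3 shows what standard follow-up contains: "Follow-up after conventional radiation will follow national guidelines and includes a history and physical every 4-6 months", with mammograms at least annually. In a separate sentence it says that the quality-of-life and cosmetic assessments "will be performed at 6 month, 1 year, and then annually through 3 years of follow-up as will digital photographs".

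Section 5.4 refers to Section 10.7, "which describes procedures and process for prematurely withdrawn subjects". Section 10.7 covers protocol amendments and says nothing about withdrawn subjects.

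Section 7.1 plans 40 patients. It calls for a review at 8 or more fair/poor of the first 20, or 12 or more of 40. It then restates this as a need for at least 29 of 40 good/excellent. It names no analysis population, missing-score rule, replacement rule or dropout allowance.

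**The concern.** After the single fraction, what remains on study is mainly data collection, including the primary endpoint at 6 to 36 months. A PI-initiated withdrawal at that stage ends the required cosmesis scoring.

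One listed reason is related to the outcome. Section 8.1 lists fibrosis, hyperpigmentation and breast atrophy among the toxicities to be captured. Appendix II scores fibrosis, pigment change, skin atrophy and volume loss. A woman withdrawn for such an event is more likely than average to be heading for a fair or poor score. Loss of that kind pushes the observed good/excellent rate upward and can weaken the 6-month review rule. A score that is not taken at its visit cannot be recovered later.

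**Working it through.** **Inputs.** From Section 7.1: true good/excellent rate 0.60 (unacceptable) or 0.80 (acceptable); boundaries 8 of 20 and 12 of 40 fair/poor; acceptability at 29 of 40; stated review probabilities 0.93 and 0.10. Assumed, because the documents give no withdrawal rate: a share w of women heading for fair/poor leaves before 6 months, and no others leave.

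**1. The plan's own figures.** With fair/poor probability f, X1 the fair/poor count in the first 20 and X2 in the second 20:

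P(review) = P(X1 ≥ 8) + Σ over x = 0 to 7 of P(X1 = x) · P(X2 ≥ 12 − x)

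- f = 0.40 gives 0.933 (stated 0.93).
- f = 0.20 gives 0.098 (stated 0.10).

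Both reproduce, with all 40 women scored.

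**2. Rate among scored women at a true 0.60.** Rate = 0.60 / [0.60 + 0.40(1 − w)].

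- w = 10%: 0.60/0.96 = 0.625
- w = 20%: 0.60/0.92 = 0.652

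**3. Chance of review at a true 0.60.** Section 7.1 does not say whether 20 and 40 are women enrolled or women scored.

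- Reading A (enrolled; a missing woman counts as not fair/poor): f = 0.40(1 − w).
- Reading B (scored): f = 0.40(1 − w) / [0.60 + 0.40(1 − w)].

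| w | f, reading A | P(review), A | f, reading B | P(review), B |
|---|---|---|---|---|
| 0 | 0.400 | 0.933 | 0.400 | 0.933 |
| 10% | 0.360 | 0.837 | 0.375 | 0.880 |
| 20% | 0.320 | 0.676 | 0.348 | 0.795 |

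In counts under reading A, 0.40 × 40 = 16 fair/poor are expected. Losing 4 leaves 12 of 36, which still triggers review; losing 5 leaves 11 of 35, which does not. At the first look 0.40 × 20 = 8 are expected, so losing one takes the expected count below the boundary.

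**4. The 29-of-40 criterion with 40 fixed.** Losing fair/poor women does not change the number scored good/excellent. At a true 0.60, P(at least 29 of 40 good/excellent) = 0.071 whatever w is. The probability of no review at either look and at least 29 good/excellent is 0.067 (w = 0), 0.069 (10%) and 0.070 (20%).

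**5. The two rules compared.** With all 40 scored, fewer than 12 fair/poor is the same as at least 29 good/excellent. With missing scores it is not: 28 good/excellent, 8 fair/poor and 4 missing gives no review at the final count but fails 29 of 40. Under reading A at a true 0.60, the chance of no review together with failure of 29 of 40 is:

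- w = 10%: (1 − 0.837) − 0.069, about 0.09
- w = 20%: (1 − 0.676) − 0.070, about 0.25

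Under reading B all 40 are scored, the rules agree, and false acceptance is 1 − P(review): 0.12 and about 0.20, against 0.067 with no loss.

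**The case against.** The strongest reply is that Section 6.4.1 only permits withdrawal. Nothing in the documents requires or expects a woman to be withdrawn for a cosmesis-related event, and no section says that withdrawn women are excluded from analysis. A reader might infer that women with poor cosmesis will leave the primary endpoint. The text does not support that; it supports a permitted risk. This part of the reply stands.

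A reader might also infer that the trial would more readily accept a poor treatment. If 29 of 40 is applied with 40 fixed, it would not: step 4 shows almost no movement, because a missing woman counts against acceptability. That stands too. It depends, however, on a denominator that 7.1 never fixes.

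Not every withdrawal is related to outcome. Pregnancy, administrative reasons and surgery outside its window are not tied to cosmesis anywhere in the documents. Section 8.1 places fibrosis, hyperpigmentation and atrophy among chronic toxicities, so the loss may bear more on the 1- to 3-year rates than on the 6-month look. Nor do the documents show that the person who withdraws a woman also scores her: Section 6 says only that a physician or mid-level provider completes the form, and the patient scores herself separately.

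There are partial safeguards. Section 8.1 requires adverse events to be recorded from consent to the end-of-study visit, Section 8.3 provides annual safety review, and Section 10.6 has the PI monitor events and outcomes. An adverse-event withdrawal would therefore be visible. None of these supplies the missing cosmesis score. The 6-month rule also leads only to a review and a decision, not to automatic closure.

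**Conclusion.** The concern holds as a permitted, outcome-related loss of the primary endpoint that nothing elsewhere in the protocol repairs. Its direction on the observed good/excellent rate is upward if adverse-event withdrawals fall mainly on women with fair/poor outcomes. Its size is a sensitivity range, not an estimate. With an assumed 10% or 20% of fair/poor women lost before 6 months at a true 0.60, the rate among scored women is overstated by 0.025 or 0.052. The chance of review drops by 0.10 or 0.26 under reading A, and by 0.05 or 0.14 under reading B.

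The effect on the final decision depends on how a missing woman is counted, and Section 7.1 leaves that open. The review rule counted over enrolled women favours the treatment; 29 of 40 with a fixed denominator does not. The plan presents them as one rule, which is true only with complete data. The change should be made because it is cheap and the lost scores cannot be recovered.

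**What to change.** 1. Replace Section 6.4.2 with: *Subjects who received the boost continue all Section 6 study assessments unless they withdraw consent for follow-up.*
2. In 7.1 and 7.2, define the analysis set as all women who received the boost, with women who go on to mastectomy reported separately, as Section 5.2 already provides.
3. In 7.1, say whether 20 and 40 are enrolled or scored women and how a missing 6-month score counts in both the 12-or-more and the 29-or-more rule. Add a sensitivity analysis that counts missing as fair/poor.
4. Correct the Section 5.4 cross-reference to 10.7.

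Missing = fair/poor should not become the primary rule without rechecking the boundaries. With 5% loss unrelated to outcome, at a true 0.80, f = 0.20 + 0.80 × 0.05 = 0.24, and the chance of review rises from 0.10 to 0.25.

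The cost is a short amendment and some continued scheduled assessments for women who would otherwise have left. Withdrawal of consent remains the subject's right, and missing scores from that source still need the rule in item 3.

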7.1 Statistical Analysis of Cosmetic Outcome

This trial will accrue a total of 40 patients over 3 years. The rate of *physician-reported* good/excellent cosmetic outcome will be estimated at baseline and at the following four follow-up time points: 6, 12, 24, and 36 months. A true rate of good/excellent cosmetic outcome rate of ≥ 0.80 would be considered acceptable, while a true rate of ≤ 0.60 would be unacceptable. The cosmetic outcome rate at 6-months will be monitored with the following rules.

Sample size	Review patient data if and when the number of patients with fair/poor cosmetic outcome at 6 months is:
20	≥ 8
40	≥ 12

Specifically, if and when 8 or more of the first 20 patients (40%) have a fair/poor outcome, or if and when 12 or more of the 40 patients (30%) have a fair/poor outcome, the data will be reviewed and a decision will be made whether to close the trial. In other words, least 29 of the 40 patients (0.725) must have a good/excellent cosmetic outcome in order to consider the cosmetic outcome rate acceptable. If the true cosmetic rate is 0.60 and 0.80, then the probability that the rules above will call for a review is 0.93 and 0.10, respectively. Assuming an observed good/excellent cosmesis rate of 0.75, a sample size of 40 will provide a 95% CI's of 0.62 – 0.88.

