3 PROTOCOL SYNOPSIS

3.1 Purpose

This protocol seeks to utilize a novel method of tumor bed boost delivery and to better understand breast cancer radiation response through the analysis of pre-and post-radiation samples.

Primary Objective:

1. Determine physician and patient-reported rates of good/excellent cosmesis at baseline and 6 months, 1, 2, and 3 years post-treatment as measured by the NRG cosmesis scale.

Secondary Objective:

1. Evaluate changes in circulating free DNA pre and post-radiation in order to identify potential blood based radiation response biomarkers.
2. Assess patient-reported Quality of Life (FACT-B) and patient satisfaction at the same time points as above (primary objective).
3. Assess local control in the treated breast relative to historical controls.
4. To review treatment plans, evaluate delivery techniques, and assess positioning verification images.

Hypotheses

We hypothesize that the boost can be delivered preoperatively to the intact breast tumor with acceptable cosmetic outcomes. Furthermore, we anticipate that pre- and post-radiation blood samples will provide an avenue for understanding breast cancer radiation response.

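### Does the plan need to name month 0 for the cosmesis visits, and a rule for reading the 12 to 36 month rates?

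*Combined protocol and SAP*

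**What the plan says.** The primary objective in Section 3.1 is to "Determine physician and patient-reported rates of good/excellent cosmesis at baseline and 6 months, 1, 2, and 3 years post-treatment". The footnote to the cosmesis row of the Section 6 table sets the visits "At baseline (prior to treatment), six months and one year after treatment and then annually for 2 additional years". Section 6.3 gives the same schedule, counted in follow-up time, within the paragraph on care after conventional radiation.

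Section 7.1 estimates the physician-reported rate at baseline and at 6, 12, 24 and 36 months. It sets a true rate of at least 0.80 as acceptable and of at most 0.60 as unacceptable, and ties neither value to a visit. It then states: "The cosmetic outcome rate at 6-months will be monitored with the following rules". The data are reviewed if 8 or more of the first 20 subjects, or 12 or more of 40, score fair or poor. In the section's restatement, at least 29 of 40 "must have a good/excellent cosmetic outcome in order to consider the cosmetic outcome rate acceptable".

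**The concern.** There are two apparent gaps.

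**Clock.** No section says which treatment starts the count. Section 5.2 allows whole-breast radiation either after systemic therapy or following surgery without it. If month 0 is the boost, a subject on the first route might be scored at 6 months before whole-breast radiation ends and be pooled with subjects scored after it. If month 0 is the last whole-breast fraction, that cannot happen, but the first look comes later. The 8/20 and 12/40 counts, which can lead to closing the trial, would then depend on an unwritten choice. A score not taken at the other time cannot be recreated.

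**Reading of later rates.** One, two and three years are also primary time points, yet the only cut-off for observed counts restates the 6-month rule. A 36-month result of 29/40 would have an exact 95% CI of 0.561 to 0.854, which contains both 0.60 and 0.80, and the plan does not say what to conclude.

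**Working it through.** **1. The plan's own figures.** Inputs from Section 7.1: looks at 20 and 40 subjects, review limits 8 and 12, true good/excellent rates 0.60 and 0.80. Let q be the fair/poor probability. Then

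P(review) = P(X20 ≥ 8) + Σ (k = 0 to 7) P(X20 = k) × P(Y20 ≥ 12 − k),

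where X20 and Y20 are independent binomial(20, q) counts for the first and second 20 subjects.

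| True good/excellent | q | First look | Second look | Total | Plan |
|---|---|---|---|---|---|
| 0.60 | 0.40 | 0.5841 | 0.3485 | 0.933 | 0.93 |
| 0.80 | 0.20 | 0.0321 | 0.0661 | 0.098 | 0.10 |

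The stated interval is the Wald interval: 0.75 ± 1.96 × √(0.75 × 0.25 / 40) = 0.75 ± 0.134, or 0.616 to 0.884 (plan: 0.62 to 0.88). The 29/40 restatement also agrees: 11 fair/poor is the most that avoids review, and 40 − 11 = 29. None of these figures uses the start of the clock.

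**2. Which event the text points to.**

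*Pointing to the boost:*
- The Section 6 table has one pre-treatment column and one follow-up column, and surgical excision is in the follow-up column. Treatment, in this table, is over before surgery.
- Baseline for cosmesis precedes treatment, hence precedes the boost.
- Surgery is timed "Within 2-4 days following radiation", which can only be the boost. The post-radiation blood draw must come before surgery, so it too follows the boost.
- The toxicity visit is an "Appointment by a radiation oncology physician/mid-level provider 1-2 months post-radiation"; Section 6.3 places the same visit "within 2 months after preoperative treatment, to evaluate for treatment toxicity".
- Sections 6.1 and 6.2 use study treatment for the step that follows screening and clip verification. Whole-breast radiation is consistently called conventional.

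*Pointing to the end of conventional radiation:*
- Section 6.3 lists the cosmesis visits in the paragraph on follow-up after conventional radiation. That paragraph also covers monitoring for locoregional recurrence, an endpoint that Section 7.2 times from the start of treatment, so placement there does not fix an origin.

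**3. What mixed scoring could do (sensitivity only).** Assume a share s of subjects is scored before whole-breast radiation ends. The overall fair/poor rate is q = (1 − s) × q_after + s × q_early, put into the formula in step 1. The shares and both rates are assumptions.

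| s | q (after 0.40, early 0.20) | P(review) | q (after 0.20, early 0.40) | P(review) |
|---|---|---|---|---|
| 0 | 0.40 | 0.933 | 0.20 | 0.098 |
| 10% | 0.38 | 0.893 | 0.22 | 0.165 |
| 25% | 0.35 | 0.803 | 0.25 | 0.301 |
| 50% | 0.30 | 0.574 | 0.30 | 0.574 |

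The assumed early/after difference, 0.20, equals the whole distance between the plan's benchmarks. The documents give no value for s, the gap to whole-breast radiation, or either rate, so the effect could be nil or of either sign.

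**4. The price of the other clock.** With even accrual, 40/36 = 1.11 subjects per month, so the 20th subject enters at month 18. Counted from the boost, that subject's 6-month score falls at month 24, with 1.11 × 24 ≈ 27 enrolled. Counted from the last whole-breast fraction, with an assumed gap of 2 to 6 months, it falls at months 26 to 30, with about 29 to 33 enrolled. The later clock makes the scores more uniform but leaves fewer subjects for the first look to protect.

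**5. Reading 36-month rates against 0.60 and 0.80, with 40 evaluable.**

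| Good/excellent | Exact 95% CI | Wald 95% CI |
|---|---|---|
| 26 | 0.483–0.794 | 0.502–0.798 |
| 29 | 0.561–0.854 | 0.587–0.863 |
| 30 | 0.588–0.873 | 0.616–0.884 |
| 31 | 0.615–0.892 | 0.646–0.904 |

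The exact interval settles neither benchmark at 27 to 30; the plan's Wald interval settles neither at 27 to 29. With 32 to 40 evaluable (an assumed range), the exact interval settles neither with probability 0.23 to 0.39 at a true 0.80 and 0.20 to 0.34 at a true 0.60. Setting later rates beside the benchmarks would therefore often leave the question open, and the answer at 30/40 would depend on the interval chosen.

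**The case for a change.** The best case for a change is that this is the time origin of a primary endpoint that also drives a review with closure as one outcome. The protocol names its event elsewhere: the start of treatment for failure times in Section 7.2, and the span from the boost to one month after conventional radiation for acute toxicity in Section 8.1. The form in Appendix II rates the result of breast conservation therapy, which Section 3.2 describes as surgery followed by radiotherapy. One phrase would end the doubt at almost no cost.

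It stands that no sentence names month 0, and that pooling scores from different stages of treatment is possible under a boost clock. The sentence in Section 5.2 on recording treatment in the ARIA system concerns boost delivery, so it does not by itself show that whole-breast dates will reach the analysis file. On the other hand, the acute-toxicity window in Section 8.1 cannot be applied without the end date of conventional radiation, so the study team must know that date.

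What does not stand is that the text is evenly divided, or that a stated figure is at risk. Writing down the month-0 event would record the reading that the schedule already supports. For the later rates, a descriptive comparison with 0.80 and 0.60 that has no reading rule would leave the same question open, and a binding rule would be a different design.

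**Conclusion.** No change to the plan follows. The clock is a missing detail, not a contradiction, and an analyst working from the Section 6 schedule would reasonably count from the boost. Sample size, review limits and operating characteristics (0.933 and 0.098) are the same under either origin, provided one rate applies to all scored subjects. The size and direction of any effect from mixed scoring cannot be found from the documents: the values in step 3 run from no effect to a review probability of 0.574, and rest wholly on assumed shares and rates. The rule leads to a data review and a decision, so those looking at the counts can take each subject's stage of treatment into account. Each origin has a cost, later detection or less uniform scores, and choosing between them is a fair trade-off for the sponsor.

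The later rates need no decision rule. The objective is to determine rates, Section 7.1 estimates them, and the 0.80 and 0.60 benchmarks, which carry no time limit, are there for any reader to apply. It is enough that the report states the origin used for the visits and the number evaluable at each one.

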Subjects will be taken to the treatment machine and positioned comfortably as they were at the time of CT simulation. Image-guidance will be used to localize the treatment volume, including on-board radiographic imaging and cone-beam CT. Cone-beam CT will always be completed except in cases where this is not technically feasible due to machine technical constraints. Positioning correction will be performed as necessary, verified and documented. Implanted marker may be considered as surrogates for effective target localization. The target localization procedure will be documented and adjustments will be made as appropriate. Treatment will be delivered to the target volume in one fraction. Each treatment plan will be checked for quality assurance in both calculation and dosimetry. All treatment will be recorded and verified through ARIA information system.

Post-operative Radiation:

Following pre-operative boost subjects will proceed to surgical resection. Systemic therapy will then be delivered as indicated and radiation will resume following systemic therapy in standard fashion. Alternatively, women will return following surgical resection and initiate conventional whole breast radiation +/- regional

nodal treatment as per standard procedures. Hypofractionated breast treatment will be considered an acceptable alternative to standard therapy (46-50Gy) when clinically appropriate.

Cosmesis, recurrence and late RT toxicities outcomes will be gathered and recorded separately for subjects deemed to require mastectomy based on unexpected findings at the time of surgical resection. It would not be accurate to compare the secondary endpoints of these subjects to those receiving breast conservation.

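### Do the two statements of the final 6-month cosmesis rule conflict when some of the 40 patients have no score?

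*Combined protocol and SAP*

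**What the plan says.** Section 7.1 fixes accrual at 40 and monitors physician-reported cosmesis at 6 months. A true good/excellent rate of 0.80 or more is acceptable, and 0.60 or less is not. Data are reviewed if 8 or more of the first 20 are fair/poor, or "if and when 12 or more of the 40 patients (30%) have a fair/poor outcome". The section then says, as a paraphrase, that at "least 29 of the 40 patients (0.725) must have a good/excellent cosmetic outcome in order to consider the cosmetic outcome rate acceptable". For true rates of 0.60 and 0.80 it states that "the probability that the rules above will call for a review is 0.93 and 0.10, respectively". A review ends in a decision on whether to close the trial; closure is not automatic.

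Three other places bear on who has a score:

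- Section 5.2: "Cosmesis, recurrence and late RT toxicities outcomes will be gathered and recorded separately for subjects deemed to require mastectomy", with the reason that "It would not be accurate to compare the secondary endpoints of these subjects to those receiving breast conservation".
- Section 6.4.1: "Subjects may voluntarily withdraw from the study at any time".
- Section 6.4.2, on follow-up after withdrawal: "Standard of care follow up will adhered to".

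No section defines an evaluable set for cosmesis, says how a missing 6-month form counts, or provides for replacement of patients.

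**The concern.** A patient without a 6-month score adds nothing to the count of 12 and nothing to the count of 29. The fair/poor statement therefore treats her as if she were not fair/poor, and the good/excellent statement as if she were not good/excellent. With 11 fair/poor, 28 good/excellent and one unscored, the first statement calls for no review and the second says the rate is not acceptable.

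Such patients are foreseeable. Mastectomy cases are set apart, although the reason given mentions only secondary endpoints while cosmesis is the primary objective (section 3.1: "Determine physician and patient-reported rates of good/excellent cosmesis at baseline and 6 months"). The form in Appendix II asks about breast conservation. Patients who withdraw are promised standard follow-up but not the cosmesis form.

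This is the only numeric decision rule on the primary endpoint. If the denominator were chosen after the data were seen, the verdict on cosmesis could turn on that choice.

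**Working it through.** **Inputs.** From section 7.1: looks at 20 and 40; limits of 8 and 12 fair/poor; fair/poor probability q = 0.40 (true good/excellent rate 0.60) and q = 0.20 (true rate 0.80). Assumed, because the documents give no rate: 1, 2 or 4 unscored, with the first 20 fully scored.

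**Formula.** Let X20 and Xn be the fair/poor counts at the two looks, and b the limit at the final look.

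P(flag) = P(X20 ≥ 8) + Σ over x = 0 to 7 of P(X20 = x) · P(Bin(n − 20, q) ≥ b − x)

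**The plan's own figures (n = 40, b = 12).**

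- q = 0.40: 0.5841 + 0.3485 = 0.9326, against the stated 0.93.
- q = 0.20: 0.0321 + 0.0661 = 0.0983 after rounding, against the stated 0.10.

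Both reproduce. With 40 scored, 11 or fewer fair/poor is the same event as 29 or more good/excellent, since 40 − 11 = 29.

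**Fewer than 40 scored.** The fair/poor statement keeps b = 12. The good/excellent statement, read as a fixed count, fails at 28 or fewer good, so b = n − 28. Every result flagged by the first is also flagged by the second, so the chance that they disagree is the difference between the two flag probabilities.

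| Scored | P(flag) at 0.60: 12-fair/poor vs 29-good | P(flag) at 0.80: 12-fair/poor vs 29-good | Disagree at 0.80 |
|---|---|---|---|
| 40 | 0.9326 vs 0.9326 | 0.0983 vs 0.0983 | 0 |
| 39 | 0.9169 vs 0.9561 | 0.0862 vs 0.1465 | 0.060 |
| 38 | 0.8985 vs 0.9735 | 0.0756 vs 0.2179 | 0.142 |
| 36 | 0.8530 vs 0.9925 | 0.0586 vs 0.4340 | 0.375 |

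**Reading the printed percentages instead of the counts.** Section 7.1 also prints the limits as proportions, 0.725 good/excellent and 30% fair/poor. At 40 these are neighbouring counts: 11/40 = 27.5% fair/poor passes and 12/40 = 30% does not. Applied to the number scored:

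| Scored | Review limit from 72.5% good | Review limit from 30% fair/poor | P(flag) at 0.80 | P(flag) at 0.60 |
|---|---|---|---|---|
| 39 | 11 | 12 | 0.1465 vs 0.0862 | 0.9561 vs 0.9169 |
| 38 | 11 | 12 | 0.1287 vs 0.0756 | 0.9445 vs 0.8985 |
| 37 | 11 | 12 | 0.1124 vs 0.0664 | 0.9304 vs 0.8772 |
| 36 | 10 | 11 | 0.1709 vs 0.0978 | 0.9557 vs 0.9135 |

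The two percentage readings differ by one patient at each of these sizes. The wide gap at 36 in the first table (0.059 against 0.434) comes from holding 29 as a fixed count while the denominator shrinks.

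**A third convention.** If every unscored patient is counted as fair/poor, the two sentences agree at any number scored: 28 good of 40 then means 12 not good. The price is the 29-good column of the first table.

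**The case for a change.** The best argument for a change is that the gap is foreseeable from the protocol itself, touches the one numeric rule on the primary endpoint, and could be closed without extra patients. One unscored patient is enough to produce opposite answers. The printed percentages do not settle it either, since 28/39 is 71.8% good/excellent (below 72.5%) while 11/39 is 28.2% fair/poor (below 30%). Settling the denominator in advance would remove any suspicion of a choice made after the fact.

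Much of this stands. The convention is unwritten, and a careful analyst should settle it before looking at the 6-month scores and report the number unscored with reasons. It does not show that the plan's rule is wrong. Section 7.1 is consistent at the size it states, and the conflict needs an added premise about missing scores that the documents do not quantify. Section 5.2 also goes part of the way: recording mastectomy cosmesis separately, with a form that asks about breast conservation, points to leaving those patients out of the rate. The reference there to secondary endpoints is loose drafting, as the preceding sentence names cosmesis.

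Nor is there a clearly better rule to adopt. Over 36 to 39 scored, the 72.5% limit raises the chance of review at a true rate of 0.80 to 0.112–0.171, above the stated 0.10. The 30% limit keeps it at 0.066–0.098, but detection at 0.60 falls to 0.877–0.917. Restricting either to scored patients could flatter cosmesis, because section 6.4.1 lists adverse events and disease progression among the reasons for withdrawal. Counting unscored patients as fair/poor guards against that but raises false reviews most.

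**Conclusion.** No change follows. The rule and its stated probabilities are correct for 40 scored patients. What is missing is a convention for patients without a 6-month score, a detail that analysts would supply sensibly. At a true rate of 0.80 the two statements disagree with probability 0.060 if one patient is unscored and 0.142 if two are. The figure of 0.375 needs four unscored and a fixed count of 29. These sizes rest on assumed numbers unscored and on a fully scored first 20.

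The consequence is small. Crossing the limit prompts a review, and a result such as 28 of 39 (0.718) would be plain to those reviewing it. The final-look disagreement can be known only once the 6-month scores are complete, after accrual, so it bears on the verdict about cosmesis and not on enrolment. Section 7.1 also estimates the rate at 6, 12, 24 and 36 months, so the reader of the results does not depend on the threshold alone.
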